11. STATISTICAL METHODS

11.1 Analysis populations

All Enrolled subjects (see Section 9.3 Study Population) will be analysed on an Intent-to-Treat (ITT) basis for the Primary and Secondary Endpoint of Safety.

For avoidance of doubt: The ITT analysis population includes all enrolled subjects who undergo attempted access site closure with Vivasure PerQseal® device (i.e. PerQseal® closure device is attempted to be placed into the vasculature and contacted the patient).

All closures from Enrolled subjects will be analysed on a modified Intent-to-Treat (mITT) basis for the Secondary Endpoint of Performance, excluding enrolled subjects which met an exclusion criteria (documented by a protocol deviation).

For avoidance of doubt: The mITT analysis population includes all closures from enrolled subjects who undergo attempted access site closure with Vivasure PerQseal® device (i.e. PerQseal® closure device is attempted to be placed into the vasculature and contacted the patient), with the exception of devices that were prevented from deploying for reasons listed in the exclusion criteria or due to issues associated with the primary procedure.

A secondary analysis population for the primary safety endpoint will include Per-Protocol (PP) for Primary Safety. The PP is a subset of the ITT analysis population with no major protocol deviations and who experienced the safety endpoint or did not prematurely withdraw from the study prior to being evaluated for the primary safety endpoint.

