- ix. **Time to Haemostasis** Time to haemostasis (TTH) is determined as the elapsed time from when the Introducer-sheath and PerQseal® closure device have been removed from the patient to first observed cessation of bleeding (excluding cutaneous or subcutaneous oozing) at the target access site arteriotomy.
- x. **Time to Ambulation** Time to Ambulation (TTA) is defined as the time from post procedure sheath removal until the patient is comfortable walking approximately 6 m.
- xi. **Time to Device Deployment** Time to Device Deployment (TTDD) is defined as the time from insertion of the PerQseal[®] closure device into the Introducer-sheath to complete removal of the PerQseal[®] closure device and Introducer-sheath from the patient following deployment.
- xii. **Overall Procedural Time** Overall Procedural Time (OPT) is defined as the time from first invasive contact with the patient's groin to completion of all aseptic procedures related to the groin.
- xiii. **Technical Success Rate** Technical Success Rate (TSR) is defined as the number of PerQseal® closure devices that are deployed and achieve haemostasis (i.e. cessation of bleeding (excluding cutaneous or subcutaneous oozing)) without need for any alternative treatment (other than manual compression or adjunctive endovascular ballooning) at target access site, divided by the total number of PerQseal® closure devices where deployment was attempted (as per the PerQseal® closure device IFU). Device malfunction resulting in alternative therapy will be considered as a technical failure.
- xiv. **Surgical Closure** Standard surgical vascular access and sutured closure.
- xv. **Baseline** Prior to interventional procedure.
- xvi. **Endovascular Aortic/Aneurysm Repair (EVAR)** Endovascular surgery used to treat an abdominal aortic aneurysm (AAA).
- xvii. **Thoracic Endovascular Aortic/Aneurysm Repair (TEVAR)** Endovascular surgery used to treat a Thoracic aortic aneurysm.
- xviii. **Transcatheter Aortic Valve Replacement (TAVR)** Procedure in which a bioprosthetic valve is inserted through a catheter and implanted within the diseased native aortic valve. Also known

as Transcatheter Aortic Valve Implantation (TAVI) or Percutaneous Aortic Valve Replacement (PAVR).

- xix. **Activated Clotting Time (ACT)** Measures the intrinsic clotting activity of whole blood in seconds.

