5.4 Delivery of the Implant

The implant has been designed to be delivered into the artery via a supplied Introducer-sheath and over a 0.014" guidewire. Hence, the delivery sequence starts with the Introducer-sheath and 0.014" guidewire *in situ* (approx. 4 cm) within the vessel.

The loading cannula (containing the implant) is first inserted into the Introducer-sheath hub. This engages the loading cannula with the sheath hub.

The Sheath-cam is rotated (Figure 1), which withdraws the Introducer-sheath, allowing the implant to unfold within the artery. The implant is then positioned against the artery wall closing the arteriotomy. Once tamponade is confirmed the guidewire is removed, the Cam lock depressed, and the Release-cam is rotated to deploy the extraarterial-pin and release the implant. This completes the deployment and seals the arteriotomy.

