9.3.1 Subject withdrawal/exclusion

A patient is enrolled in the study by signing an Ethics Committee approved Informed Consent Form; if he/she meets all eligibility criteria (both pre-procedure and during the procedure) and there is intent to close the femoral artery puncture site using the PerQseal® and the PerQseal® closure device contacts the patient¹.

Patients on whom the PerQseal[®] closure device is not used due to failure to meet eligibility criteria/withdrawal of consent are considered not enrolled in the study. Patients not exposed to the PerQseal[®] closure device will not require additional post procedure, pre-discharge or post discharge follow-up assessments and will not be included in safety and performance analyses. For

¹ The PerQSeal® closure device is considered to have contacted the patient if the loading cannula of the PerQSeal® closure device is inserted into the Introducer sheath.

enrolled patients that have received exposure to the PerQseal[®] closure device, but the device was not deployed for reasons other than device failure their data will be included in safety, but not performance analyses and all post procedure, pre-discharge and post discharge follow-up assessments will be performed.

A patient may withdraw from the study at any time if he/she decides to do so. However, all data collected to the time of withdrawal will be recorded in the worksheet, with a note to indicate that the patient has withdrawn their consent to further participate in the study. No further follow-up or data will be recorded for that patient on the worksheet or eCRF. Note that routine management and standard practice of care should continue for the patient without prejudice.

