11.7 Secondary endpoints

Two secondary endpoints will be summarised for the entire group of subjects/closures:

-Minor device related vascular access site complications per subject up to 1 months (safety endpoint)

-Technical success rate for the PerQseal® closure device at discharge per closure is no worse than the technical success rates associated with the 'perclose' or 'preclose' technique following EVAR or TAVR.

The criteria for successful performance of the investigational device have been aligned with what is reported within the literature, ensuring a like for like comparison. A literature based performance control is the only effective source of data available for this study, as it is not applicable to compare the performance of a device with that of a surgical technique of cut-down and sutured closure, used for the safety control. Therefore, the performance of the PerQseal® (i.e. the proportion of successful closures) will be assessed by comparison of the proportion of PerQseal® closures which achieve acute haemostasis at the arteriotomy site and do not lead to alternative treatment (other than manual compression or adjunctive endovascular ballooning) (Pperformance) from the mITT group against a performance goal for performance (PGperformance). This will be achieved by testing for non-inferiority against a performance non-inferiority limit (NLP), which is the predetermined PGperformance minus a non-inferiority margin delta. In order to claim non-inferiority against a performance driven PGperformance the lower bound of a (95%) confidence interval for the proportion of successful "Pperformance" (using the exact method for estimating a Binomial proportion) must be shown to be greater than the non-inferiority limit.

The PG_{performance} and non-inferiority margin delta have been derived from a Meta-analysis of performance rates for percutaneous device closure (Prostar® XL and Perclose ProGlide®) from comparable patient populations reported in the literature.

The proportion with successful closure is estimated to be 0.84 with a 95% Confidence Interval of 0.81 to 0.87. Given that the lower bound is 0.81 this justifies the use of 0.84 as valid $PG_{performance}$ minus a non-inferiority margin of 0.03 yielding an overall non-inferiority limit (N_{LP}) of 0.81 for performance.

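### SAP 11.1 defines the mITT set for the technical-success test in two incompatible ways, and near the 0.81 limit a single closure can reverse the verdict

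*SAP*

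**What the plan says.** SAP 11.7 compares the proportion of successful closures "from the mITT group against a performance goal for performance". The exact lower confidence limit must exceed 0.81, which is the 0.84 goal minus a margin of 0.03.

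SAP 11.1 describes the mITT set in two consecutive paragraphs:

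- The first takes all closures from enrolled subjects, "excluding enrolled subjects which met an exclusion criteria (documented by a protocol deviation". The unit removed is the subject, and deployment is not mentioned.
- The second, offered as a clarification, removes only "devices that were prevented from deploying for reasons listed in the exclusion criteria or due to issues associated with the primary procedure". The unit removed is the device, and removal depends on non-deployment. Primary-procedure issues are not defined.

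Three other places bear on who is counted:

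- SAP 9.3.1, on patients exposed to the device: if "the device was not deployed for reasons other than device failure their data will be included in safety, but not performance analyses". This works by patient and does not use the term mITT.
- SAP 9.3 counts each limb as a separate closure for the performance analysis.
- SAP 4.2 xiii gives the technical success rate as successes "divided by the total number of PerQseal® closure devices where deployment was attempted (as per the PerQseal® closure device IFU". It adds: "Device malfunction resulting in alternative therapy will be considered as a technical failure".

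**The concern.** An analysis set for a pass/fail test has to say, closure by closure, who is in. The two sentences in 11.1 give different answers for the same closure, so an analyst could follow either and be faithful to the SAP. The study is single-arm and unblinded, and the decision to stop a deployment and the reason recorded for it are made by people who know the outcome. Removal that depends on non-deployment can only take out non-successes, so it can only raise the rate. The result at stake is the claim that performance is no worse than suture-mediated closure.

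The exposure has limits. A malfunction that leads to alternative therapy is a technical failure under 4.2 xiii. The opening is therefore for stopped attempts put down to other causes, and for deployed closures in subjects later found ineligible.

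**Working it through.** **Step 1. Apply each rule to the same closure.**

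| Closure | 11.1, first sentence | 11.1, second sentence | 9.3.1 |
|---|---|---|---|
| (a) Deployed, subject has an exclusion-criterion deviation | out | in | in |
| (b) Not deployed because of a primary-procedure issue, no deviation | in | out | out, unless it counts as device failure |
| (c) Not deployed for another non-device reason, no deviation | in | in | out, unless it counts as device failure |

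Rows (a) and (b) settle the conflict within 11.1: the second sentence puts back closures that the first removes, and removes closures that the first keeps. The qualifier in the last column is needed because 4.2 viii defines Device Failure by whether closure failed and needed interventional or surgical correction, so some stopped attempts may fall under it.

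**Step 2. Inputs for the size of the effect.** Limit 0.81 and exact binomial method (SAP 11.7). One-sided 0.025, power 0.90, stated minimum 44 closures, 75 subjects planned (SAP 10). I assume 75 closures; bilateral treatment could make it more.

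**Step 3. The plan's own figure.** SAP 10 does not give the success rate behind the 44 closures. With 44 closures the exact test needs at least 41 successes. At a true rate of 0.96, P(X ≥ 41) = 0.902, so 44 is consistent with an assumption of about 0.96. The figure is not in dispute.

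**Step 4. Where the verdict turns.** For x successes in n closures, the lower limit L(x, n) is the 0.025 quantile of Beta(x, n − x + 1). The test passes if L > 0.81.

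| Successes/closures | L | Result |
|---|---|---|
| 68/75 | 0.8171 | pass |
| 67/75 | 0.8006 | fail |
| 67/74 | 0.8148 | pass |
| 65/72 | 0.8099 | fail |

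- *Row (b) case.* 75 closures, 67 successes, one of the 8 non-successes a primary-procedure stop, no deviations. The first sentence keeps it: 67/75, fail. The second removes it: 75 − 1 = 74, so 67/74, pass.
- *Row (a) case.* 75 closures, 68 successes, three of them in subjects with exclusion-criterion deviations. The second sentence keeps them: 68/75, pass. The first removes them: 68 − 3 = 65 and 75 − 3 = 72, so 65/72, fail.

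The choice of sentence can therefore move the verdict either way.

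**Step 5. How often it would matter.** Let p be the true rate over 75 closures and let each failure be removed independently with probability d. The pass probability is the sum over s and k of Bin(s; 75, p) × Bin(k; 75 − s, d), taken where L(s, 75 − k) > 0.81. The values of d are assumptions; the documents give none.

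| True rate p | d = 0 | d = 0.10 | d = 0.20 | d = 0.30 |
|---|---|---|---|---|
| 0.81 | 0.018 | 0.039 | 0.070 | 0.128 |
| 0.90 | 0.521 | 0.632 | 0.724 | 0.802 |
| 0.96 | 0.990 | 0.994 | 0.997 | 0.999 |

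At 0.90, removing 10% of failures adds 0.632 − 0.521 = 0.111. At 0.96, removing 30% adds 0.9986 − 0.9898 = 0.0088. The first row is not a false-positive rate for the mITT proportion: with d = 0.20 that proportion is itself 0.81 / (0.81 + 0.19 × 0.8) = 0.842.

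**The case against.** The strongest defence is that the second sentence merely clarifies the first. It does not, since rows (a) and (b) go in opposite directions. A related defence is that 9.3.1 makes eligibility a condition of enrolment, so ineligible enrolled subjects should not exist. In that case the first sentence removes nobody, row (a) disappears, and row (b) still separates the two sentences.

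Other objections stand, and they rule out stronger readings that a reader might infer:

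- *That 4.2 xiii flatly contradicts 11.1.* An analysis set may narrow the denominator of a measure. Enrolment turns on contact: the device "is considered to have contacted the patient if the loading cannula of the PerQSeal® closure device is inserted into the Introducer sheath". This is the opening move of delivery in SAP 5.4: "The loading cannula (containing the implant) is first inserted into the Introducer-sheath hub". Whether it is already a deployment attempt depends on the IFU, which is not among the documents.
- *That 9.3.1 is a third mITT definition, wider than the others.* It does not name the mITT set. Under 4.2 viii, a stopped attempt that ends in correction could count as device failure and stay in.
- *That the chance of landing on 66 or 67 of 75 (26.5% at a true rate of 0.90) is the chance of a changed verdict.* Removable stops must also be present among the failures. Step 5 gives the relevant figure.
- *That omissions would go unseen.* Tables 1 and 4 give closure counts and the technical-success denominator, and SAP 11.11 requires deviations to be listed and assessed for their influence. What is missing is a closure-by-closure reason.
- *That the primary-procedure exception must go.* SAP 11.7 says its success criteria were aligned with the literature, but the denominators behind 0.84 are not given. Counting procedure-related stops as failures also has a price: at a true rate of 0.96, power with 75 closures falls from 99.0% to 96.8%, 92.4% or 85.7% if an assumed 1%, 2% or 3% of attempts stop for that reason.

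**Conclusion.** The contradiction within SAP 11.1 is real, and 9.3.1 needs to be aligned with it. It also leaves a bilateral patient with one deployed and one stopped device without clear handling, because 9.3.1 works by patient and performance is counted by limb.

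Its practical weight depends on where the true rate lies. Near 0.96, the rate that the 44 closures imply, the pass probability shifts by at most about 1 percentage point over the assumed 10% to 30% removal. Near 0.90 it goes from 0.52 to 0.63 with 10% removed. These figures assume 75 independent closures and the exact one-sided 0.025 test.

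This is a secondary endpoint that does not drive the sample size, and dropped closures stay in the ITT safety analysis. The documents do not show which denominator is right. They show only that the SAP has not settled on one.

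**What to change.** Before analysis, replace the two mITT sentences in 11.1 and the performance wording in 9.3.1 with one rule, applied closure by closure, that states:

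1. whether a deployed closure in a subject who met an exclusion criterion stays in;
2. which non-deployments are removed;
3. what counts as a primary-procedure issue, consistent with Device Failure in 4.2 viii.

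Report technical success over all closures where deployment was attempted (4.2 xiii) as a labelled sensitivity analysis, with the start of an attempt written into the SAP. Add a listing of every closure left out of the performance analysis, with its reason. The sponsor should justify the primary denominator against those in the literature behind 0.84. SAP 11.10, which refers to implanted subjects for technical success, should be brought into line.

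The cost is SAP wording, one extra analysis and one listing. The sensitivity rate may come out slightly below the mITT rate, because it can include stops unrelated to the device.

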11.2 Time points of analyses

A report will be completed once the primary endpoint and all 3 months follow-up assessments has been reached for all subjects included or remaining in the study. This report will be shared with Ethics Committees, Competant Authorities and other relevant parties. A full study termination report will be produced if the study is terminated prior to completion for any reason or at the exit of all enrolled subjects from the study.

An interim analysis may be performed once sufficient subjects have completed their primary safety endpoint to ensure the study has at least 80% power.

11.3 Statistical methods

For continuous variables, the mean, median, standard deviation, interquartile range and minimum-maximum value will be presented. In order to compare subgroups, the differences in means of the subgroups will be tested with a two-sample t-test (in case of 2 subgroups) or with one-way ANOVA (in case of >2 subgroups) in case the assumptions for the required tests are valid. If these assumptions are violated, testing will be done using independent samples Mann-Whitney U tests or Kruskal-Wallis tests (instead of one-way ANOVA).

For categorical variables counts and percentages will be presented. In order to compare differences between subgroups, categorical variables with an expected cell count of at least 5 in 80% of the cells (but no zero expected cell counts) will be tested using the Pearson chi-square test. For categorical variables that do not have an expected cell count of at least 5 in 80% of the cells (or that do have at least one zero expected cell count) and require the differences between the two treatment groups to be tested, the following will be done: Fisher's exact test will be performed for 2x2 contingency tables or the likelihood ratio test will be performed for larger contingency tables.

The tests for all subgroup comparisons assume a significance level of 0.05. No adjustment for multiple testing will be done for any of these variables, as these do not consider the primary endpoint.

Specification for the test concerning the primary endpoint can be found in Section 11.6.

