8. STUDY DESIGN

This study will be a prospective, multi-centred, non-randomized study to investigate the safety and performance of the PerQseal® in 75 patients in approximately 10 European investigational sites. The study shall not be blinded prior to, during or post the procedure. All patients undergoing an endovascular procedure requiring an arteriotomy created by 12 to 20 F sheaths, via the common femoral artery will be screened against the inclusion/exclusion criteria.

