11.4 Baseline characteristics

Demographic and baseline characteristics shall be tabulated and summarised for the study. The following characteristics will also be tabulated and summarised both per centre and per procedure type:

-Age

-BMI

- -Gender
- -Procedural ACT
- -Sheath size
- -Sheath size to femoral artery diameter ratio
- -Hypertension
- -Diabetes
- -Severe acute non-cardiac systemic disease, autoimmune disease or terminal illness
- -Bleeding Diatheses
- -Clinically significant peripheral vascular disease

Subgroup comparisons will be tested and the results of these tests will be summarised by their respective p-values. As the primary endpoint will be analysed per centre and per procedure type (among others), we will compare the above baseline characteristics between these subgroups as well, in order to further explore any possible confounders for the relationships between the primary endpoint and both the centre and the procedure type.

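### For sparse tables larger than 2x2, SAP 11.3 specifies a likelihood-ratio test that does not hold its stated 0.05 level: about 7–10% for common characteristics by centre, under 1% for rare events

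*SAP*

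**What the plan says.** SAP 11.3 sets a three-way rule for categorical subgroup comparisons.

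- Pearson chi-square is used for "categorical variables with an expected cell count of at least 5 in 80% of the cells", provided that no expected count is zero.
- Otherwise, "Fisher's exact test will be performed for 2x2 contingency tables".
- Otherwise, for anything bigger, "the likelihood ratio test will be performed for larger contingency tables".

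On the level, 11.3 says: "The tests for all subgroup comparisons assume a significance level of 0.05". On multiplicity it says: "No adjustment for multiple testing will be done for any of these variables".

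SAP 11.4 applies the rule to the baseline characteristics by centre and by procedure type: "Subgroup comparisons will be tested and the results of these tests will be summarised by their respective p-values". It gives the reason, which is to look for confounders: "As the primary endpoint will be analysed per centre and per procedure type (among others"). The results go into Table 8 (baseline) and Table 3 (primary endpoint). A footnote to Table 3 allows it to be left out if major complications are few, without giving a threshold. SAP section 8 plans the study "in 75 patients in approximately 10 European investigational sites".

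**The concern.** The rule leaves Pearson's test because its large-sample approximation is doubtful with small counts. For 2x2 tables it moves to an exact test, which answers that doubt. For larger tables it moves to another statistic that, on the natural reading, is referred to the same large-sample chi-square distribution. The larger tables here are sparser than the 2x2 ones, so the protection is missing where it is needed most.

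The p-values are meant to show whether centre or procedure type could confound the primary result. If their true level is above 0.05, chance imbalances between centres are flagged too often. If it is far below 0.05, real clustering of a rare complication in one centre can go unseen.

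**Working it through.** **Inputs.** From the SAP: 75 patients and about 10 centres (section 8), level 0.05 and the 80% / expected-count-5 rule (11.3), four procedure groups (Tables 3 and 8), and a 5% planning rate for major complications (section 10), so 75 × 0.05 = 3.75 expected events. Assumed, because the documents do not give them: prevalence of the baseline characteristics, centre sizes and the procedure mix.

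**Step 1: which test is reached.** A 10 × 2 table has 20 cells, and 80% of 20 is 16. Expected counts add up to 75, but 16 cells with at least 5 each need 16 × 5 = 80. The Pearson branch therefore cannot be reached with 10 centres, whatever the prevalence or centre sizes. With 9 centres, 80% of 18 is 14.4, so 15 cells are needed. They would use all 15 × 5 = 75 and leave zeros elsewhere, which the rule also bars.

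**Step 2: the actual level.** The plan's figure is 0.05. To test it, events were drawn as Binomial(nᵢ, p) with the same p in every centre, 200,000 tables per setting. The statistic G² = 2 Σ O ln(O/E) was compared with the 0.95 quantile of chi-square on 9 degrees of freedom, 16.92. Centre sizes were near-equal (7–8 each), skewed (20, 14, 10, 8, 6, 5, 4, 3, 3, 2) or very skewed (30, 15, 9, 6, 4, 3, 3, 2, 2, 1).

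| True prevalence | Near-equal | Skewed | Very skewed |
|---|---|---|---|
| 20% | 9.1% | 7.2% | 6.0% |
| 30% | 9.5% | 9.4% | 8.6% |
| 50% | 8.8% | 10.5% | 10.7% |
| 70% | 9.6% | 9.3% | 8.6% |

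At 10–15% prevalence the range over all layouts is 2.5–7.3%, which straddles the nominal level. At 5% it is 0.64–0.84%, and at 2% it is 0.03–0.13%. The 0.05 is therefore not reproduced at either end.

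**Step 3: a rare-event example.** Suppose that 3 events occur and all fall in one centre of 7 patients. The expected count of events there is 7 × 3/75 = 0.28.

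G² = 2 [3 ln(3/0.28) + 4 ln(4/6.72) + 68 ln(75/72)] = 2 [7.115 − 2.075 + 2.776] = 15.63

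This is below 16.92 (p about 0.075). It is the most extreme table possible with 3 events and near-equal centres, so the test cannot reject. The exact probability that all 3 fall in the same centre, with five centres of 7 and five of 8, is [5 × C(7,3) + 5 × C(8,3)] / C(75,3) = (175 + 280)/67,525 = 0.0067. An exact p-value for this table is therefore at most about 0.007.

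**Step 4: procedure type.** With assumed four-group splits of 75 patients, the likelihood-ratio test rejects about 5–9% of the time at 20–70% prevalence and about 2–4% at 5%. The direction is the same, but the departure is smaller.

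**Step 5: the alternatives.**

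- *Pearson.* With near-equal centres it would reject 4.2–4.4% at 10–50% prevalence, better than the test that replaces it. With skewed centres and a 5% rate it rejects about 8–12%, so simply keeping Pearson is not safe.
- *Exact conditional test.* With 10 near-equal centres its size is 0.048–0.050 for 11–37 events and 0.007–0.049 for 2–8 events, never above 0.05.

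**The case against.** The case against giving this much weight is good, and most of it stands.

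- *Prevalence.* A reader might infer that every centre comparison runs at twice the stated level. The documents do not support that, because they give no prevalences, and near 10–15% the level is about right. Three of the six binary variables in Table 8 (severe systemic disease, bleeding diathesis, peripheral vascular disease) are also restricted by exclusion criteria i, iii and iv. Inflation is most plausible for gender, hypertension and diabetes.
- *Table 3.* A reader might infer that the primary endpoint by centre will be tested in this way. Its footnote allows omission when complications are few, and about four events are expected. That is a partial answer only, since no threshold is set.
- *Procedure type.* It should not be given the centre figures. The effect there is milder.
- *The word asymptotic.* The SAP does not use it. It is an inference, though a natural one: Fisher's test is called exact in the same sentence and the likelihood-ratio test is not.
- *Number of centres.* Ten is approximate. At 11–37 events the rejection rate of the likelihood-ratio test is about 6–9% with 6 near-equal centres and about 7.5–11% with 12.
- *Consequences.* No decision rule hangs on these p-values, and they are unadjusted for multiplicity by design. A further 4 or 5 percentage points per test adds modestly to false positives that are already expected.

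What survives is narrower. For centre tables the rule always selects this test, and the test does not have the level that the SAP states.

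**Conclusion.** The concern holds as a minor defect in the choice of test. With 10 centres and 75 patients, the likelihood-ratio test is the only one reachable for centre by a binary variable. Read as asymptotic, it rejects about 7–10% of null tables at an assumed prevalence of 20–70% with near-equal or skewed centres (6–11% if very skewed centres are included). It rejects about 3–7% at 10–15%, and under 1% at the 5% planning rate. Procedure-type tables depart less.

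The result rests on the assumed prevalences, centre sizes and procedure splits, and on the asymptotic reading. It does not reach the trial's main conclusion, although a reader might infer otherwise from the link to the primary endpoint in 11.4. SAP 11.6 tests non-inferiority with an exact binomial interval, which does not depend on these comparisons.

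**What to change.** In SAP 11.3, replace the likelihood-ratio test for sparse tables larger than 2x2 with the Fisher-Freeman-Halton exact test. Where full enumeration is too slow, allow a Monte Carlo p-value with the number of replicates and the seed stated. It would help to add that no test is made when a category has no events, since the zero-count clause now sends such a table to a test that cannot be informative.

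The cost is one or two sentences, a different option in standard software and slightly more computing. The exact test is somewhat conservative with very few events. No data collection, sample size or primary analysis changes.
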